## **10.5 Final Response Assessment**

Overall survival is measured as the time from the date of diagnostic biopsy which confirmed disease to the date of death from any cause. Patients not known to have died at last follow-up are censored on the date they were last known to be alive. Patients will be followed for a minimum of one year from the completion of the treatment.

Patients who go on to allogeneic transplant will be censored for survival on the dates that they start conditioning regimen to avoid transplant as a confounding factor in analysis of overall survival.

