Study Outcome Measures	
Safety
 
 
• Common Terminology Criteria for Adverse Events (CTCAE) version 5.0
 
• Adverse events
 
• Serious adverse events
 
• Adverse events leading to discontinuation of study therapy
 
 
Efficacy
 
 
• Event-free survival
 
• Objective response rate → complete remission (CR) plus complete remission with incomplete hematologic recovery (CRi)
 
• Relapse free survival
 
• Duration of response
 
• Time to return of normal hematopoiesis
 
• Overall survival
 
• Proportion of patients who go on to receive allogeneic HSCT
 
 
Exploratory outcome measures
 
 
• Determine if MRD status can be used as a surrogate marker for survival
 
• Determine if using gene expression profiling can identify subset of patients who are more likely to respond
 

Rationale	
In the phase III trial of CPX-351 versus 7+3 chemotherapy for first line treatment of secondary AML in patients 60-75 years of age, 309 patients were treated with either of the two regimen. There was a statistically significant improvement in overall survival as well as overall remission rate in the CPX-351 arm.
 
Glasdegib in combination with LDAC has been shown to have tolerable side effect profile while improving survival outcomes in some patients with elderly AML who are unfit for chemotherapy. In the phase II trial of Glasdegib with cytarabine and daunorubicin, 69 patients with newly diagnosed AML were treated with the combination. The overall survival of the combination was improved to historical controls.
 
We hypothesize that the combination of CPX-351 with Glasdegib will demonstrate improvements in event-free survival as well as being well tolerated.

**Study Title: Phase II study of the combination of Glasdegib and CPX-351 in previously untreated patients with Acute Myelogenous Leukemia with MDS related changes or therapy-related Acute myeloid leukemia: A University of California Hematologic Malignancies Consortium Protocol (UCHMC1913/UCI 18-105)**

**PI:** [name], Assistant Clinical Professor of Medicine

**Institution:** Chao Comprehensive Cancer Center, University of California Irvine, Orange, CA

UCHMC1913/UCI 18-105  

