**Footnotes:**

- A Must be obtained before undergoing any protocol-specific study procedures, unless as part of standard of care
- B Serum beta-HCG should be done for any female of child-bearing potential
- C Bone marrow collections do not need to be repeated if a diagnostic bone marrow procedure was done prior to informed consent and is done within 28 days of starting day 1 of induction
- D Collect bone marrow aspirate for research sample for gene expression correlatives; if patient has any circulating blasts, then peripheral blood can be collected instead of aspirate; if bone marrow is a “dry tap,” then this sample does not need to be collected
- E Re-induction is based on response evaluation bone marrow done on day 20 of induction. If there is greater than 5% blast count, re-induction is recommended. The final decision for re-induction is based on investigator’s discretion. For patients who will be treated with re-induction, an ECHO and pregnancy test (for female patients of child-bearing potentials) will be done before starting re-induction
- F Omit CPX-351 on day 5 for participants receiving re-induction

G ECG is done pre-dose and can be done up to 24 hours before planned glasdegib dosing

H During induction, repeat an ECG a week after starting glasdegib (around day 13-15). If clinically significant abnormal ECG or clinically significant changes in QTc, then refer to section 6.4 for further guidance. If normal or non-clinically significant abnormalities and/or changes in QTc, additional ECG monitoring is not required and is done per the treating investigator's discretion

I Glasdegib should continue until day 1 of the next cycle of CPX-351

J Up to two cycles of consolidation is allowed. These are 28 day cycles, unless delays are necessary. In the case of a delay, glasdegib will continue daily until the start of CPX-351 infusion in the next cycle. If the patient will proceed to allogenic SCT, then consolidation can be skipped or shorten. Glasdegib will be stopped at least 7 days before transplant.

K These are 28 days cycle. Patients who are not receiving HSCT will be allowed to proceed to glasdegib maintenance for up to 1 year of study start

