### **1.5.3 Further development of CPX-351**

In the phase II trial, the outcomes were compared of CPX-351 versus traditional cytarabine/daunorubicin (7+3) chemotherapy in 126 patients with newly diagnosed AML [32]. CPX-351 had higher response rates than traditional cytarabine/daunorubicin (7+3) chemotherapy at 66.7% versus 51.2% with p=0.07 which met the predefined criteria of p<0.1. There was a prolongation of event-free survival as well as overall survival but this was not significant. The recovery after cytopenias were more prolonged after CPX-351 with more grade 3-4 infections but without increased deaths due to infection. Aside for risk of infection, patients did have diarrhea, nausea, edema, constipation, rash, febrile neutropenia. However, these side effects were also seen with the cytarabine/daunorubicin arm. Furthermore, the 60-day mortality was not increased in the CPX-351 arm. This provided the rationale for a phase III trial.

In the phase 3 clinical trial, CPX-351 has improved overall survival rates, event-free survival and response rate (complete response and complete responses with incomplete recovery) to traditional 7+3 chemotherapy in the patients with previously untreated AML with MDS related changes as well as AML evolving out of MDS [33]. There was a prolongation in recovery of cytopenias seen again. There were similar rates of grade 3-5 infections between CPX-351 and standard cytarabine/daunorubicin induction chemotherapy. At median follow-up of 21 months, the median overall survival was 9.5 months in CPX-351 arm versus 5.9 months in the standard 7+3 arm. The complete remission/complete remission with incomplete recovery (CR/CRi) rate were 47% with CPX-351 versus 33% in 7+3 arm (p=0.008). The duration of remission was similar between the two groups at 6.9 months versus 6.1 months in CPX-351 and 7+3 arm, respectively. As a result of improved response rates, more patients receiving CPX-351 were also able to go to transplant than 7+3 arm at 34% versus 25% p=0.049 [34]. Furthermore, as an exploratory endpoint, there was improved post-transplant survival in patients who received CPX-351 versus 7+3 chemotherapy [35].

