### **5.6 Allogenic stem cell transplantation**

The decision to go to allogeneic transplant once the patient is in remission is based on the treating's physician discretion as well as the desire of the patient. Patients who are considered candidates for allogeneic transplant and have a donor stem cell source available can proceed to allogeneic transplant. Alternatively, patients can receive up to two cycles of consolidation chemotherapy prior to allogeneic transplant.

For patients going to transplant, Glasdegib will be discontinued within 7 days prior to start of conditioning for their transplant.

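### Overall survival is defined as death from any cause, but transplanted patients are censored at conditioning; transplant is decided in remission, so the censoring is informative

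*Combined protocol and SAP*

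**What the plan says.** Section 10.5 gives the endpoint: "Overall survival is measured as the time from the date of diagnostic biopsy which confirmed disease to the date of death from any cause". Its general censoring rule is "Patients not known to have died at last follow-up are censored on the date they were last known to be alive". The next paragraph adds an exception: patients who go on to allogeneic transplant are "censored for survival on the dates that they start conditioning regimen to avoid transplant as a confounding factor in analysis of overall survival".

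On who is transplanted, Section 5.6 states: "The decision to go to allogeneic transplant once the patient is in remission is based on" physician discretion and the patient's wish. On timing, footnote J of the Schedule of Events adds: "If the patient will proceed to allogenic SCT, then consolidation can be skipped or shorten".

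Section 13.4.2.3 analyses OS by Kaplan-Meier, log-rank and, where assumptions allow, Cox models. It names no OS analysis that runs through transplant, and no competing-risk or time-dependent handling of transplant. Survival follow-up after transplant continues under footnote M and Sections 5.9 and 7.4.

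**The concern.** A death after conditioning never counts under this rule, so the analysed quantity is not the all-cause endpoint defined one paragraph earlier.

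Kaplan-Meier also needs censored patients to have the same future risk as those still under observation. Here the censored patients are in remission by design. Section 1.1 itself attributes poor long-term survival partly to low remission rates, so the protocol treats remission as prognostic. Removing remitters leaves a risk set weighted towards non-remitters. The curve would describe survival without transplant, which is presumably what avoiding confounding means here, only if being transplanted were unrelated to prognosis.

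At stake are the reported OS curve, its median and its 12-month value, and any comparison with OS figures not censored at transplant. OS has no decision rule. The sentence in Section 10.5 concerns survival only, so the six-month event-free survival test in Section 13.2.3 is unaffected by it.

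**Working it through.** The plan gives no OS target or OS power figure, so there is nothing to reproduce first. The check is how far the planned estimator lies from the two quantities it might be meant to estimate.

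**Inputs from the documents**
- 30 evaluable patients (Section 13.3).
- From the phase III background in Section 1.5.3: CR/CRi "rate were 47% with CPX-351 versus 33% in 7+3 arm (p=0.008"; "more patients receiving CPX-351 were also able to go to transplant than 7+3 arm at 34% versus 25" percent; median OS 9.5 months with CPX-351, taken as not censored at transplant.
- Number censored: 0.34 × 30 = 10.2, about 10 patients. This is a guide only. The source trial was "for first line treatment of secondary AML in patients 60-75 years of age", while Section 3.1 enrols from age 18.
- Conditioning window: about month 1 (remission at day 28, consolidation skipped) to 28 + 75 + 55 + 55 = 213 days, or 7.0 months from biopsy. This uses the screening window and the cycle limits in Section 5.4, without reinduction.

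**Assumptions**
- Exponential survival. Remitters' death hazard is k times the non-remitters' hazard λ, with k = 1/4, 1/3 or 1/2.
- All transplants are in remitters, with conditioning uniform over months 1 to 7.
- HR is the post-transplant hazard relative to remitters not transplanted.
- λ is solved so that all-cause median OS is 9.5 months.

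**One case in full: k = 1/3, HR = 1, 34% transplanted**
1. All-cause survival is S(t) = 0.47·exp(−kλt) + 0.53·exp(−λt). Setting S(9.5) = 0.50 gives λ = 0.1166 per month.
2. True 12-month OS: 0.47·exp(−0.466) + 0.53·exp(−1.399) = 0.295 + 0.131 = 42.6%.
3. To have 34% of all patients reach conditioning alive, a fraction q = 0.843 of remitters must be transplant-bound.
4. Risk set at month 7:
   - Surviving non-remitters: 0.53·exp(−0.816) = 0.234. Surviving remitters: 0.47·exp(−0.272) = 0.358.
   - The true remitter share is 0.358/0.592 = 60%.
   - After censoring, the remitters left are 0.358 × (1 − 0.843) = 0.056, a share of 0.056/0.290 = 19%.
5. The large-sample Kaplan-Meier limit is exp(−∫h(t)dt), where h is the average hazard in the censored risk set. At 12 months it is 33.6%, with an estimated median of 8.0 months.
6. Bias: 33.6 − 42.6 = −9.0 points. At HR 1 the transplant does nothing, so this is also the error against survival without transplant.

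**12-month bias against all-cause OS (points)**

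| Transplanted | HR | k=1/4 | k=1/3 | k=1/2 |
|---|---|---|---|---|
| 34% | 0.5 | −15.1 | −14.0 | −12.0 |
| 34% | 1 | −10.7 | −9.0 | −6.1 |
| 34% | 1.5 | −7.3 | −5.3 | −1.9 |
| 34% | 4 | +2.9 | +5.5 | +9.3 |
| 25% | 0.5 | −9.5 | −8.9 | −7.8 |
| 25% | 1 | −6.5 | −5.5 | −3.8 |
| 25% | 1.5 | −4.1 | −2.9 | −0.8 |
| 25% | 4 | +3.3 | +5.0 | +7.5 |

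At 34% the sign changes at HR 3.1, 2.5 and 1.8 for k = 1/4, 1/3 and 1/2. Against survival without transplant, the error over this grid is −11.1 to −4.9 points at 34% and −6.6 to −3.3 at 25%.

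**Cross-checks**
- 4,000 simulated trials of 30 patients (34%, k = 1/3, HR 1) give a mean shift of −8.9 points. The standard error of 12-month OS is √(0.426 × 0.574/30) = 0.09.
- A second simulation assumed remitter and non-remitter medians of 18 and 5 months, transplant at months 2 to 5 and HR 1. The censored estimate is 31.0% and the truth 39.8%.
- Control with equal prognosis (both medians 9.5 months): the censored curve recovers survival without transplant (41.6% against 41.6%). It still misses all-cause OS when transplant changes the hazard (41.7% against 46.8% at HR 0.5; 41.6% against 37.8% at HR 1.5).

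**The case against.** The rule is deliberate and its reason is stated. Section 1.2 cites a series that also censored at transplant, so there is precedent, and which OS version leads is partly a choice of estimand. Section 2.2 collects survival follow-up for OS with no transplant exception, and Section 13.4.2.1 promises to examine the data in many ways, so nothing bars an uncensored curve. This stands as far as it goes, but none of it overrides the specific rule in Section 10.5. The data sets in Section 13.4.2.1 settle who is analysed, not when they are censored.

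The stronger objection is to the numbers. No document gives survival by response status, so the range for k is assumed. With k = 0.7, at 34% transplanted, HR 1 understates all-cause OS by only 3.3 points and HR 1.5 overstates it by 1.1. The error against survival without transplant falls to about 3 to 4 points. Transplanting 34% of patients when 47% remit means 0.34/0.47 = 72% of remitters, and the model needs 79 to 90% of them to be transplant-bound because some die first. Section 1.5.3 does not say that every transplant was in remission. With k = 1/4 and HR 1 the model's remitter median is about 21 months, which is not reconciled with the 6.9-month remission duration quoted there. These points limit the size and leave the mechanism intact.

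The shift is also about one standard error at n = 30. That is true, but it is systematic and would not shrink with more patients.

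**Conclusion.** The concern holds. Followed as written, Section 10.5 yields an OS curve that is not all-cause survival. It is also not survival without transplant wherever remitters outlive non-remitters.

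The conflict in the text is certain; the size is illustrative. Under the stated model with k between 1/4 and 1/2 and 34% transplanted, 12-month OS is understated by 6 to 11 points if transplant has no effect on survival and by 2 to 15 points for HR 0.5 to 1.5. At HR 4 it is overstated by 3 to 9. At 25% transplanted and HR 1 the understatement is 4 to 7 points. The direction against all-cause OS cannot be known in advance, because it depends on post-transplant mortality. This should be corrected, but it concerns a secondary endpoint and does not alter the go/no-go decision.

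**What to change.** In Sections 10.5 and 13.4.2.3, make the main OS analysis time from diagnostic biopsy to death from any cause. Follow transplanted patients through transplant and censor only at the date last known alive, which is already the rule for everyone else. Keep the version censored at conditioning as a labelled sensitivity analysis, with a note that it assumes transplant is unrelated to prognosis. If the effect of transplant itself is examined, treat it as a time-dependent covariate or use a landmark.

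The cost is wording in two sections and one extra analysis. No visit, procedure or data item is added, because post-transplant survival is already followed. The trade-off is that the main OS result will include whatever transplant contributes, and the report should say so.

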## **11.0 ADVERSE EVENTS**

All adverse events will be graded as toxicity using the CTCAE version 5.0 grading system. Graded toxicity should be recorded in the CRF.

Analyses will be performed for all patients having received at least one dose of study drug.

## 11.1 Event Definitions

- **Adverse event (AE)** - An adverse event is any untoward medical experience or change of an existing condition that occurs during or after treatment, whether or not it is considered to be related to the protocol intervention. An AE can therefore be any unfavorable and unintended sign (including a clinically significant abnormal laboratory finding), symptom, or disease temporally associated with the use of an experimental intervention, whether or not related to the intervention.
- **Unexpected Adverse Event** [Modified from the definition of unexpected adverse drug experience in FDA regulations at 21 CFR 312.32 (a)] – An adverse event is unexpected if it is not listed in the investigator’s brochure and/or package insert; is not listed at the specificity or severity that has been observed; is not consistent with the risk information described in the protocol and/or consent; is not an expected natural progression of any underlying disease, disorder, condition, or predisposed risk factor of the research participant experiencing the adverse event.
- **Expected Adverse Event** - Any event that does not meet the criteria for an unexpected event OR is an expected natural progression of any underlying disease, disorder, condition, or predisposed risk factor of the research participant experiencing the adverse event.
- **Serious Adverse Event (SAE)** [21 CFR 312.32] - defined as any expected or unexpected adverse event that result in any of the following outcomes:
  - Death
  - Is life-threatening experiences (places the subject at immediate risk of death from the event as it occurred)
  - Unplanned hospitalization equal or greater than 24 hours)) or prolongation of existing hospitalization
  - A persistent or significant disability/incapacity
  - A congenital anomaly/birth defect
  - Any other adverse event that, based upon appropriate medical judgment, may jeopardize the subject’s health and may require medical or surgical intervention to prevent one of the outcomes listed above (examples of such events include allergic bronchospasm requiring intensive treatment in the emergency room or at home, blood dyscrasias or convulsions that do not result in inpatient hospitalization, or the development of drug dependency or drug abuse).
- **Unanticipated problem (UP)** - Any incident, experience or outcome that meets all three of the following criteria:
  1. Unexpected (in term nature, severity, or frequency) given the following: a) the research procedures described in the protocol-related documents such as the IRB approved research protocol, informed consent document or Investigator Brochure (IB); and b) the characteristics of the subject population being studied; AND
  2. Related or possibly related to participation in the research (possibly related means there is a reasonable possibility that the incident, experience, or outcomes may have been caused by the drugs, devices or procedures involved in the research); AND
  3. Suggests that the research places subjects or others at greater risk of harm (including physical, psychological, economic, or social harm) than previously known or recognized.
- **Protocol Violation**- A protocol violation is an accidental or unintentional change to or noncompliance with the IRB-approved protocol that increases risk or decreases benefit and/or affects the subject's rights, safety, welfare, and/or the integrity of the data.

Examples of incidents that may be considered violations include: enrolling a participant who does not meet the inclusion criteria; obtaining verbal consent before the initiation of study procedures when the IRB requires signed, written informed consent; and failure to collect screening labs before initiation of study procedures [Reference: Policy #57 UCI HRPP Policy and Procedure Glossary].

- **Protocol Deviation-** a protocol deviation is an accidental or unintentional change to the research protocol that does not increase risk or decrease benefit or have a significant effect on the participant's rights, safety or welfare, or on the integrity of the data. Deviations may result from the action of the participant, researcher, or staff. Examples: a rescheduled study visit, an omitted routine safety lab for a participant with previously normal values; or failure to collect an ancillary self-report questionnaire data (e.g., quality of life) [Reference: Policy #57 UCI HRPP Policy and Procedure Glossary].

## 11.2 Adverse Event Monitoring

All patients who have received at least one dose of CPX-351 will be considered evaluable for safety. After initiation of study drug, all adverse events (AEs) and serious adverse events (SAEs) regardless of attribution will be collected at every visit until 28 days following the last administration of study drug, until study discrimination/termination, or until initiation of subsequent anticancer therapy, whichever comes first. Subjects will be assessed at each follow-up visit to determine if there are any new AEs. Adverse events will no longer be reported in patients who go on to allogeneic transplant. AEs and SAEs will be recorded on the adverse event report section within OnCore. Please reference section 11.3 and 11.4 for a complete list of all entities who require notifications of AEs and SAEs.

Adverse event data collection and reporting, which are required as part of every clinical trial, are done to ensure the safety of subjects enrolled in the studies as well as those who will enroll in future studies using similar agents. Adverse events are reported in a routine manner at scheduled times during a trial. Additionally, certain adverse events must be reported in an expedited manner to allow for optimal monitoring of patient safety and care.

As far as possible, each adverse event should be evaluated to determine:

- duration (start and end dates)
- severity (grade)
- seriousness
- relationship to study agent
- action taken (i.e., none, study agent modification, medical intervention)
- outcome (i.e., resolved without sequelae, resolved with sequelae, ongoing)

Adverse events monitoring begins after initiation of study treatment and ends 28 days following the last administration of study treatment or study discontinuation/termination, whichever is earlier.

All patients experiencing an adverse event, at least possibly related to the drug, will be monitored until:

- the adverse event resolves or the symptoms or signs that constitute the adverse event return to baseline;
- any clinically significant abnormal laboratory values have returned to baseline;
- there is a satisfactory explanation other than the study drug for the changes observed; or
- death.

### 11.2.1 Severity

All non-hematologic adverse events will be graded according to the NCI Common Terminology Criteria for Adverse Events (CTCAE) version 5.0. The CTCAE v5.0 is available at <http://ctep.cancer.gov/reporting/ctc.html>

If no CTCAE grading is available, the severity of an AE is graded as follows:

Mild (grade 1): the event causes discomfort without disruption of normal daily activities.

Moderate (grade 2): the event causes discomfort that affects normal daily activities.

Severe (grade 3): the event makes the patient unable to perform normal daily activities or significantly affects his/her clinical status.

Life-threatening (grade 4): the patient was at risk of death at the time of the event.

Fatal (grade 5): the event caused death.

